**SKIN IRRITATION SCORING SYSTEM (Draize)**

Erythema	0	No reaction
	1	Mild and/or transient redness limited to sensitive area
	2	Moderate redness persisting over much of the product-exposed area
	3 *	Severe redness extending over most or all of the product-exposed area
Edema	0	No reaction
	1	Mild and/or transient swelling limited to sensitive area
	2	Moderate swelling persisting over much of the product-exposed area
	3 *	Severe swelling extending over most or all of the product-exposed
Rash	0	No reaction
	1	Mild and/or transient rash limited to sensitive area
	2	Moderate rash persisting over much of the product-exposed area
	3 *	Severe rash extending over most or all of the product-exposed area
Dryness	0	No reaction
	1	Mild and/or transient dryness limited to sensitive area
	2	Moderate dryness persisting over much of the product-exposed area
	3 *	Severe dryness extending over most of all of the product-exposed area

\* A score of 3 in one or more of the conditions evaluated represents significant irritation and qualifies as an Adverse Event.

**22.2 Adverse Events**

Adverse Events will be documented for all subjects from the time the Clipping appointment procedures complete to the time of discharge from the study. Adverse Events will be categorized in relationship to the product that was applied to the specific skin site. In case of a medical emergency, 911 will be called from the laboratory facility and general first aid administered until Emergency Medical Service arrives. Medical facilities/personnel are in close proximity.

In the event that either the Principal Investigator or the Sponsor determines that continuation of the study poses a hazardous risk of serious injury or death to the subjects, the study will be stopped.

**14.3.1 Definitions**

**14.3.1.1 Adverse Event/Experience**

An Adverse Event/Experience is any unexpected or undesirable experience occurring to a subject during a study, which may or may not be related to a test material. All Adverse Event/Experiences will be recorded and reported using Adverse Event Form according to the Standard Operating Procedures of the Testing Facility.

All Adverse Events, regardless of severity or the cause/effect relationship, are to be recorded. The severity of the effect will be noted as "Mild," "Moderate," or "Severe" according the following definitions:

Mild                      Awareness of sign(s) or symptom(s), but easily tolerated.

Moderate	Discomfort to a degree as to cause interference with normal daily life activities and /or requiring medication.
Severe	Incapacity with inability to work or do usual daily life activities and requiring medical attention/intervention.

**14.3.1.2 Causal Relations of Adverse Event/Experience**

When determining the causal/effect relationship to a test material, the relationship will be described as "None," "Possible," "Probable," or "Definite." The following definitions will be utilized:

None	No association to a test material. Related to other etiologies such as concomitant medications or conditions or subject's known clinical state.
Possible	Uncertain association. Other etiologies are also possible.
Probable	Clear-cut association with improvement upon withdrawal of a test material. Not reasonably explained by the subject's known clinical state.
Definite	An adverse event with a clear-cut temporal association with exposure to study materials and cannot reasonably be explained by the subject's known clinical state. Association with study material is confirmed by laboratory if possible.

**14.3.1.3 Serious Adverse Event/Experience – During this Study**

A Serious Adverse Event/Experience is any adverse experience occurring that results in any of the following outcomes:

- Death;
- A life-threatening adverse drug experience;
- Inpatient hospitalization or prolongation of existing hospitalization;
- A persistent or significant disability/incapacity;
- Congenital anomaly/birth defect;
- An important medical event that may require medical or surgical intervention to prevent one of the previously listed outcomes.

**14.3.1.4 Unexpected Adverse Event/Experience**

An Unexpected Adverse Event/Experience is any adverse drug event/experience not listed in the current labeling for a test material or the current investigator's brochure. Where test product labeling or investigator's brochure is not available, anticipated experiences will be based on the known pharmacological/toxicological properties of a test material or ingredients.

### 14.3.2 Follow-up

If an adverse event/experience related to the study procedures or study product occurs, the Sponsor will be monetarily responsible for all costs associated with the follow-up for said event including, but not limited to, medical visits and medication prescribed by a medical professional directly related to the adverse event along with an administration fee that covers the Principal Investigator's time resolving the Adverse Event. If it is determined by Test Facility Management that the Adverse Event is due to negligence on the part of the Test Facility, no cost will be passed through to the Sponsor. The subject under the direction of the Principal Investigator (or designee) may be referred to the nearest acute care facility for treatment. All Adverse Events will be followed to resolution and documented on appropriate Adverse Event paperwork.

### 14.3.3 Notification

The Sponsor and the reviewing IRB will be notified of all adverse event/experiences that require treatment within 2 business days. Any Serious or Unexpected Adverse Event/Experience that occurs during the study must be reported immediately by the Principal Investigator (or designee) to the Sponsor and the reviewing IRB, followed by written notification within 1 business day of the information being reported to the investigative study team.

#### **Sponsor Notification of Serious Adverse Event:**

[REDACTED]

[REDACTED]

The Principal Investigator, [name], and Medical Expert, [REDACTED], are required to review all unanticipated problems involving risk to volunteers or others, serious adverse events, and all subject deaths associated with the protocol and provide an unbiased written report of the event. At a minimum, the Principal Investigator and Medical Expert must comment on the outcomes of the event or problem, and in the case of a serious adverse event or death, comment on the relationship to participation in the study.

#### 14.4 Anticipated Reactions

The risks associated with this test are primarily related to application of the test materials, and/or the test methodology. Mild abrasion may occur due to cylinder sampling. Folliculitis may be present from clipping. Mild skin irritation is anticipated and in some cases mild to heavy erythema, swelling, itching, cracking, peeling, or in rare cases, blistering and/or an allergic reaction might occur.

#### 15.0 STATISTICAL METHODS

Data processing and statistical analysis for this study will be conducted by the BD statistical group based on the final monitored data provided by BSLI to the BD statistical group.

Details of the statistical analysis will be provided in a separate statistical analysis plan.

##### Data sets analyzed

The full Intent to Treat (ITT) data set (all randomized subjects) will be used for the safety analysis.

A modified Intent to Treat (mITT) data set will be used for efficacy analyses. Inclusion for the mITT data set is evaluated for each body area (left and right for the inguen and abdomen). For each body area, if the treatment day baseline bacterial count requirements are in the range of 3.00 to 5.50  $\log_{10}/\text{cm}^2$ , inclusive, on the abdomen and 5.00 to 7.50  $\log_{10}/\text{cm}^2$ , inclusive, on the inguen, then the data are included in the mITT data set. Data collected will be excluded from Per Protocol data if the treatment-day baseline counts are outside the acceptable range. Analyses conducted on the mITT data set will also be conducted on the Per Protocol data set as supportive analyses when Per Protocol data are different from mITT data.

- For  $\log_{10}$  CFU/ $\text{cm}^2$  determinations, missing data will not be imputed for either mITT data or Per Protocol data and will be excluded from analysis.
- For responder rate calculations from 6-hour data, missing data will be treated as non-responders in the mITT data, while in the Per Protocol data, missing data will not be imputed and will be excluded from the responder rate Per Protocol analysis.

## 15.1 Primary Analysis

An Analysis of Variance (ANOVA) of the baseline  $\log_{10}$  CFU/cm^2 values will be performed separately for abdomen and inguen to determine whether the randomization resulted in treatment arms with similar treatment day baseline CFU/cm^2 values.

The primary purpose of the study is to compare the immediate antimicrobial activity of the Investigational Products to the Negative Control and Active Control according to the methods described in the FDA TFM using the statistical analyses outlined in the deferral letters published by the FDA on January 19, 2017. A linear regression model will be used for primary analysis. In the model, the response is the post-treatment  $\log_{10}$  bacterial counts and predictors are the treatment effect and the pre-treatment  $\log_{10}$  bacterial counts as a covariate. The interaction between the treatment and pre-treatment  $\log_{10}$  bacterial counts will also be explored. If there is no significant interaction detected between treatment and pre-treatment  $\log_{10}$  bacterial counts, the interaction term will be removed from the model and the average difference between treatments will be estimated from the linear regression model after correcting for pre-treatment  $\log_{10}$  bacterial counts. If there is a significant interaction detected between treatment and pre-treatment  $\log_{10}$  bacterial counts, the average difference between treatments will be estimated from the linear regression model after averaging over the interaction term. The objective is to achieve a mean treatment effect ( $\log_{10}$  reduction) for Investigational Products no less than that for the Active Control by more than 0.5  $\log_{10}$  and at least 1.2  $\log_{10}$  greater than that for the Negative Control on both the abdomen and inguen. The 95% confidence intervals will be summarized for each product tested, grouped by anatomical site and each post-application time point (30 seconds and 10 minutes) and compared to the non-inferiority margin of 0.5  $\log_{10}$  for Investigational Products vs. Active Control and compared to the superiority margin of 1.2  $\log_{10}$  for Investigational Products vs. Negative Control.

It is expected that the treatment effects will meet the standards outlined above, however this is a Phase II study to inform design of future efficacy studies and is not designed to provide statistically powered evidence of efficacy.

## 15.2 Secondary Analysis

The secondary purpose of the study is to determine the persistent antimicrobial activity of the Investigational Products, Negative Control and Active Control.  $\log_{10}$  bacterial counts at 6 hours for each treatment site will be converted to a binary (yes or no) success measure with success defined as having skin flora counts that are less than or equal to the baseline skin flora counts. The objective is to demonstrate a success proportion  $\geq 95\%$  on both the abdomen and the inguen with 95% confidence. Mean responder rates along with 95% confidence intervals will be calculated for each treatment at each post-treatment time point (one-proportion test with Score method, two-sided). The mean responder rates and the corresponding confidence interval lower bounds will be compared to 95%.

### 15.3 Exploratory Analyses

#### Log Reductions:

The following descriptive statistics for  $\log_{10}$  CFU/cm^2 reductions will be computed for the mITT and Per Protocol populations for each product tested, grouped by anatomical site and each post application sampling time point (30 seconds, 10 minutes and 6 hours): mean, median, standard deviation, minimum, maximum, and count.

Antimicrobial activity will be compared using  $\log_{10}$  reductions between both Investigational Products, Active Control, and Negative Control for each anatomical area at both post treatment sampling times. Differences in  $\log_{10}$  CFU/cm^2 reductions between treatments and confidence intervals for will be produced by an Analysis of Variance (ANOVA). In the ANOVA model, the response is the  $\log_{10}$  reduction and the predictors are treatment and time point as well as the interaction between treatment and time point. The average difference in log reduction between treatments per time point will be estimated. However, all conclusions for the treatment effect (difference between treatments in  $\log_{10}$  reduction) will be based on the primary analysis only.

#### Microbial Baseline Effects:

Additional analyses may be conducted using the same methods as for the primary and secondary analysis using the Per Protocol data set, but with modified baseline requirements to determine the effect of baselines on the outcomes.

#### Product Expression Volumes:

The weight (grams) of drug product solutions applied to a treatment area will be estimated as:

Product weight prior to treatment (g) – product weight post-treatment (g)

The following descriptive statistics for expression volumes will be computed for each product tested at each anatomical site: mean, median, standard deviation, minimum, maximum, and count. An analysis of variance (ANOVA) of the applied volumes will be performed separately for each body site to determine whether the test materials had similar volumes applied. If a significant difference is found, differences between groups will be examined by appropriate follow up tests. Analysis for product expression volumes will be based on the mITT data / Per Protocol data.

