#### Microbial Baseline Effects:

Additional analyses may be conducted using the same methods as for the primary and secondary analysis using the Per Protocol data set, but with modified baseline requirements to determine the effect of baselines on the outcomes.

Product Expression: The weight (grams) of drug product solutions applied to a treatment area will be estimated as:

Product weight prior to treatment (g) – Product weight post-treatment (g)

Descriptive statistics will be generated for expressed products, and will include: mean, median, standard deviation, minimum, maximum and sample size for each test material. An analysis of variance (ANOVA) will also be performed on the expressed volumes to determine whether the treatments had similar volumes applied. Differences between groups, if found to be significant, will be examined by performing additional follow up tests. The analysis will be based on the mITT / Per Protocol data.

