7.3 Analysis Methods

For each body site, when per-protocol data are different from mITT data for average treatment effect (ATE), responder rate, log reduction or product expression volumes, per-protocol analysis and mITT analysis will be performed separately using the same statistical methods. The following analysis methods will be applied to both per-protocol analysis and mITT analysis, both abdomen and groin.

An alpha level of 5% (two-sided) is used for all analyses.

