7.3.3.3 Product Expression Volumes/Weight

An analysis of variance (ANOVA) of the applied volumes/weight will be performed separately for each body site based on mITT data and/or per-protocol data. In the model, there will be a random subject effect, a fixed body side (left or right) effect, a fixed treatment effect and the interaction between fixed effects. ANOVA table will be checked to see whether the treatment has a significant effect on product expression volumes as well as the interaction. If a significant difference is found, subgroup comparisons with Tukey’s method will be made to determine which pair of comparisons shows significant difference.

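### Whether the test materials were applied in similar amounts is to be judged by an ANOVA test of no difference, with no confidence interval for any difference and no limit for 'similar'

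*Protocol*

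**What the plan says.** Protocol 7.3 (Product Expression) plans an ANOVA of the expressed amounts "to determine whether the treatments had similar volumes applied". Protocol 15.3 (Product Expression Volumes) repeats the aim, with the ANOVA "performed separately for each body site to determine whether the test materials had similar volumes applied", and continues: "If a significant difference is found, differences between groups will be examined by appropriate follow up tests".

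SAP 7.3.3.3 gives the model: "there will be a random subject effect, a fixed body side (left or right) effect, a fixed treatment effect", plus the interaction of the fixed effects. The decision step is: "ANOVA table will be checked to see whether the treatment has a significant effect on product expression volumes as well as the interaction". The follow-up is: "If a significant difference is found, subgroup comparisons with Tukey’s method will be made to determine which pair of comparisons shows significant difference". SAP 7.3 sets the level: "An alpha level of 5% (two-sided) is used for all analyses".

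Two further facts bear on the point:

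- **Descriptive summaries are planned.** Protocol 7.3 and 15.3 list mean, median, SD, minimum, maximum and count by product, and 15.3 gives them per anatomical site. SAP 7.3.3.1 adds LSMeans.
- **Intervals are planned elsewhere.** SAP 7.3.1 compares confidence bounds with the 0.5 and 1.2 log10 margins. The exploratory log-reduction comparison (Protocol 15.3; SAP 7.3.3.2, Table 10) also reports differences with confidence intervals.

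**The concern.** Asking whether amounts were similar is an equivalence question. The ANOVA tests the null hypothesis of no difference, so a non-significant result means only that a difference was not detected. Noisier weights make that result more likely. The rule can also err the other way: with very tight weights it will flag a small difference as significant. Neither outcome tells the reader how far apart the amounts could be. That needs an estimated difference with its interval, which is not planned when the F test is non-significant and is not mentioned even when it is significant.

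The question has some substance here because delivery differs between arms. In the Protocol's application instructions, the Negative Control applicator is not pre-filled: its sponge is dipped into 3 mL of saline in a dish. The other three materials come as ready-to-use 3 mL applicators. At stake is how well the report can describe how closely the applied amounts matched, which is useful in a study meant to inform later trials.

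**Working it through.** **Design count (reproduced).** SAP 3.3 has 6 product pairs with 12 subjects each: 6 × 12 = 72 subjects and 72 × 2 = 144 sites per region. Each product is in 3 pairs: 3 × 12 = 36 sites per arm. This agrees with SAP Table 1.

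**Inputs.** From the documents: 4 arms, n = 36 per arm (a minimum), alpha 0.05. Not in the documents, and therefore assumed: CV of expressed weight 10% to 30%, within-subject correlation 0 to 0.6, and a true shortfall of 10% or 15% in one arm.

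**Step 1: plain four-group ANOVA.** With one arm low by a fraction d, the arm deviations from the overall mean are -3d/4 (once) and +d/4 (three times). Their squares sum to (9 + 3)/16 × d² = 0.75d². The noncentrality is λ = 36 × 0.75 × (d/CV)² = 27(d/CV)². The test has 3 and 140 df and a critical F of 2.669.

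| CV | λ at d = 10% | Non-significant, d = 10% | Non-significant, d = 15% |
|---|---|---|---|
| 10% | 27.0 | 0.5% | about 0% |
| 15% | 12.0 | 17% | 0.5% |
| 20% | 6.75 | 44% | 9% |
| 25% | 4.32 | 63% | 27% |
| 30% | 3.0 | 73% | 44% |

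The reverse error follows from the same formula. At CV 5%, a true shortfall of only 5% also gives λ = 27 and is flagged in 99.5% of trials.

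**Step 2: the random-subject model.** I repeated the calculation by generalised least squares for the actual layout (12 subjects per pair, side and treatment effects, F with 3 and 100 df). For d = 10%, the chance of a non-significant result is:

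| Within-subject correlation | CV 20% | CV 30% |
|---|---|---|
| 0 | 45% | 74% |
| 0.3 | 36% | 68% |
| 0.6 | 15% | 53% |

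Adding the SAP's side-by-treatment interaction with about 65 error df changes these by no more than about 1 percentage point.

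**Step 3: observed shortfall that stays non-significant.** For one low arm, F = 27(d/SD)²/3 = 9(d/SD)². Setting this to 2.669 gives d = √(2.669/9) = 0.545 SD. That is 5.4% of the mean at CV 10%, 10.9% at CV 20% and 16.3% at CV 30%.

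**Step 4: what an interval would add.** Treating sites as independent, the 95% CI half-width for a pairwise difference is 1.977 × CV × √(2/36) = 0.466 × CV. This gives 4.7%, 7.0%, 9.3% and 14.0% of the mean at CV 10%, 15%, 20% and 30%. For example, at CV 20% an observed shortfall of 8% in one arm is below the 10.9% threshold and so non-significant. Its interval would be -8% ± 9.3%, or -17.3% to +1.3%. The F test reports only the absence of significance; the interval shows that a sizeable shortfall has not been excluded.

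**The case against.** The strongest reply is that this is loose wording on an exploratory item. Means, SDs, counts and LSMeans by product are already planned, so a shortfall would be visible whatever the F test says, and a reader could build a rough interval. No CV is given. At CV 10% a 10% shortfall is almost always detected, and at CV 20% a 15% shortfall is detected about 91% of the time even by the plain ANOVA. A fixed limit could also be hard to meet: at CV 20% the half-width is already 9.3%.

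Much of this stands. It rules out three stronger readings that a reader might infer:

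- **That a material applied 10% to 15% low would be reported as similar.** The documents give no variability for expressed weight, and no rule says that non-significance will be reported as similarity. That step is implied by the stated aim only.
- **That the F test is the only information on applied amount.** The descriptive summaries are planned as well. The F test is the only planned inference when it is non-significant.
- **That the efficacy contrasts would be read as made at equal amounts.** No text ties them to this analysis. SAP 3.4 lists product expression as exploratory, and the primary model does not name expressed amount as a term.

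The reply does not justify using a no-difference test to answer a similarity question. An interval built by hand from arm means and SDs would also ignore the pairing within subjects that the SAP models.

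**Conclusion.** The point holds as a mismatch between the stated aim and the planned inference in Protocol 7.3 and 15.3 and SAP 7.3.3.3. A non-significant ANOVA cannot show that amounts were similar, and the plan has neither an interval nor a limit to do so.

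The size depends on assumptions that the documents cannot settle. For a true 10% shortfall in one arm, the chance of a non-significant result runs from under 1% (CV 10%) to about 73% (CV 30%) with independent sites. It is lower if a subject's two sides correlate: 36% at correlation 0.3 and 15% at 0.6, both at CV 20%. More than 36 sites per arm would reduce it further.

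This is a minor improvement to an exploratory analysis. The primary analysis judges confidence bounds against its margins and is unaffected.

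**What to change.** In SAP 7.3.3.3, and to match in Protocol 7.3 and 15.3:

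1. From the mixed model already specified, report each IP - AC and NC - IP difference in applied amount, per body site, with a 95% CI, regardless of the ANOVA p-value.
2. State that a non-significant ANOVA is not evidence of similarity.
3. Either have the sponsor prespecify a similarity limit, or drop the word 'similar' and call the comparison descriptive. Any limit needs a common unit: the amounts are weighed in grams, and weights of the alcohol-based solutions and of saline are not directly comparable as volumes. The sponsor should choose the limit with the half-widths above in view.

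The cost is a few sentences and one extra table from the same fitted model, with no new data. The small downside is that, with noisy weights, the result may read as similarity not shown where the ANOVA would have read as no difference.
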